3.2. Endpoints

3.2.1. Primary Outcome Measure

- The time from randomization until initial clinical resolution of Norovirus symptoms for at least 48 hours through 180 days.

Clinical resolution will be assessed from the daily diary by the subject and will be defined as:

- Cessation of vomiting and,
- No stools classified by the Bristol Stool Chart as diarrhea (Type 6 or 7)

3.2.2. Secondary Efficacy Outcome Measures

- Time from randomization to first negative viral load through 180 days.
- The change in viral titer between Day 1 and 180.

3.2.3. Secondary Safety Outcome Measures

- Incidence of unsolicited non-serious adverse events through 60 days.
- Incidence of laboratory adverse events (White Blood Cell Count (WBC), Hemoglobin, Platelet Count, Creatinine, Alkaline Phosphatase, Alanine Aminotransferase (ALT), Aspartate Aminotransferase (AST), Blood Urea Nitrogen (BUN), and Bilirubin) through 60 days.
- Incidence of protocol-specified serious adverse events through 60 days.

- Incidence of hospitalization through 60 days.

3.2.4. Exploratory Outcome Measures

- Time from randomization to initial clinical improvement in Norovirus disease through 28 and 180 days for at least 48 hours, as defined by:
 - 50% reduction in number of episodes of vomiting and,
 - Improvement in PO intake, as judged by the subjects and,
 - 50% reduction in the number of episodes of diarrhea as classified by the subject by the Bristol Stool Chart as type 6 or 7 bowel movements.
- Time from randomization to initial cessation of vomiting through Day 180 (recurrent vomiting will be considered disease recurrence unless determined to be due to another etiology [i.e. GVHD]).
- Time from randomization to subject report of no loss of appetite that is maintained for 48 hours through Day 180 (measure will be first time that the subject reports that they have no “loss of appetite” on their daily diary).
- Time from first dose to initial cessation of diarrhea through Day 180 classified by the Bristol Stool Chart as type 6 or 7 bowel movements (recurrent diarrhea will be considered disease recurrence unless determined to be due to another etiology [i.e. GVHD]).
- Time from randomization to 50% reduction in the amount of antimotility agents utilized by the subject through Day 180.
- Number of days of diarrhea through Days 28 and 180.
- Number of stools classified by the Bristol Stool Chart as type 6 or 7 bowel movements through Day 28.
- Number of days of IV hydration or total parenteral nutrition (TPN) therapy through Day 28.
- Total number of days of hospitalization through Days 28 and 180.
- Change in patient-reported quality of life as measured by EuroQOL-5 (global) and IBSQOL (diarrhea specific) [adult] or EuroQOL-5 Peds (global) and PedsQL GI Module [children] from baseline to Day 180.
- Change in patient-reported physical function as measured by NIH PROMIS Physical Function (Adult) Pediatric Global Health (Peds) from baseline to Day 180.
- Change in patient-reported emotional distress as measured by the NIH PROMIS Depression, Anxiety, Fatigue (Adult and Peds) from baseline to Day 180.
- Change in patient-reported gastrointestinal symptoms as measured by the NIH PROMIS GI (Adult and Peds) symptoms (6 of 8 subscales) from baseline to Day 180.
- The effect of co-pathogens, as determined by the BioFire stool pathogen screen, on the primary outcome measure.
- Time from randomization until initial clinical resolution of Norovirus symptoms for at least 48 hours through Day 180. Clinical resolution will be assessed from the daily diary by the subject and will be defined as cessation of vomiting and no stools classified by the Bristol Stool Chart as diarrhea (Type 6

or 7) from the total population compared to the subgroup of subjects who do not report chromaturia (discoloration of urine) based on unsolicited self-reporting.

- Incidence of unsolicited non-serious adverse events through 60 days, laboratory adverse events (WBC, Hemoglobin, Platelet Count, Creatinine, Alkaline Phosphatase, ALT, AST, BUN, and Bilirubin) through 60 days, protocol-specified serious adverse events through 60 days, and hospitalization through 60 days from the total population compared to the subgroup of subjects who do not report chromaturia (discoloration of urine) based on unsolicited self-reporting
- Time to ≥ 1 log reduction in stool Norovirus genome copies.
- Change in quantitative Norovirus load in the stool between Day 1 and Day 7, 14, 21, 28, 60, 120, and 180.
- Change in Norovirus sequence from Day 1 to Days 28 and 60.
- The effect of co-pathogens, as determined by the BioFire stool pathogen screen, on the time from randomization to first negative viral load through 180 days.
- Time from randomization to first negative viral load through 180 days and the change in viral titer between Day 1 and 180 from the total population compared to the subgroup of subjects who do not report chromaturia (discoloration of urine) based on unsolicited self-reporting.
- Change in Norovirus-specific serum and stool IgA, IgM and IgG between Day 1 and Days 28 and 60.
- Association between change in total lymphocyte count and T cell subsets at Day 1 and 180 and clinical resolution of Norovirus symptoms.
- Association between change in total lymphocyte count and T cell subsets at Day 1 and 180 and undetectable quantitative norovirus PCR.
- Association between change in Norovirus-specific serum and stool IgA, IgM and IgG from Day 1 to Days 28 and 60 and clinical resolution of Norovirus symptoms.
- Association between change in Norovirus-specific serum and stool IgA, IgM and IgG from Day 1 to Days 28 and 60 and undetectable quantitative Norovirus PCR.
- For subjects consenting to PK draws, concentrations of nitazoxanide metabolites (tizoxanide and tizoxanide glucuronide) 1 to 4 hours after the first dose on Day 7 and 10 minutes before the second dose on Day 21.
- Time to allograft rejection as per each center team.
- Time to allograft loss as reported to United Network for Organ Sharing (UNOS).
- Time to death.
- Time to withdrawal from the study because of intolerance or drug related adverse events.
- Correlation of secretor status as defined by phenotype and genotype, separately, and clinical resolution of Norovirus as defined by the primary endpoint.

3.3. Study Definitions and Derived Variables

Diarrhea:

Diarrhea will be defined as Type 6 or 7 on the Bristol Stool chart.

Baseline Value:

The baseline value will be defined as the last value obtained prior to the first dose of study product unless otherwise noted.

Additional Nitazoxanide:

Any nitazoxanide reported as a concomitant medication will be considered additional nitazoxanide.

Initial Clinical Resolution of Norovirus Symptoms:

Clinical resolution of Norovirus symptoms will be assessed from the daily diary by the subject and will be defined as:

- Cessation of vomiting and,
- No stools classified by the Bristol Stool Chart as diarrhea (Type 6 or 7).

Subjects will need to have at least two consecutive daily diary entries where they reported no vomiting, no Bristol Stool Type 6, and no Bristol Stool Type 7 to meet the criteria for initial clinical resolution. There are several variables in the daily diary that indicate whether the subject had diarrhea or vomiting for that day.

Daily Diary Diarrhea Questions:

- Phase 1 (Treatment Phase):
 - Number of Bristol Type 6 stools? (Quantitative)
 - Were there too many Bristol Type 6 stools to count? (Qualitative)
 - Number of Bristol Type 7 stools? (Quantitative)
 - Were there too many Bristol Type 7 stools to count? (Qualitative)
- Phase 2 (Longitudinal Phase):
 - Did you have diarrhea today? (By diarrhea, we mean at least ONE bowel movement that could be described as Type 6 or 7.) (Qualitative)

Daily Diary Vomiting Questions:

- Phase 1 (Treatment Phase):
 - Did you have to take another dose because you threw up the first dose within 1 hour? (Qualitative)
 - How many times did you vomit today? (Quantitative)
- Phase 2 (Longitudinal Phase):
 - Did you vomit today? (Qualitative)

For a day to count towards clinical resolution during the treatment phase, the following responses must be recorded in the daily diary entry:

- Both quantitative diarrhea questions must be 0

- Both qualitative diarrhea questions must be missing (i.e. not “yes”)
- The quantitative vomiting questions must be 0
- The qualitative vomiting question must be “no”

For a day to count towards clinical resolution during the longitudinal phase, the following responses must be recorded in the daily diary entry:

- The qualitative diarrhea question must be “no”
- The quantitative vomiting question must be 0

If a daily diary entry is missing, refer to the imputation rules in Section [6.5](#).

Viral Load:

As Norovirus surveillance laboratories have observed that Norovirus type GII is predominant compared to Norovirus type GI and dual infection by both GI and GII viruses is rare, all specimens are tested for Norovirus GII viral load first ([name], [name], person communication). Only specimens that are negative for Norovirus GII viral load will be tested for Norovirus GI viral load. Subjects will only be analyzed for the viral load test type (Norovirus GII or Norovirus GI) that they tested positive for at baseline (Visit 01). If a subject initially tested positive for GI and later tested positive for Norovirus GII before they tested negative for Norovirus GI, the subject will be considered positive for Norovirus GI until they test negative for Norovirus GII and Norovirus GI. Subjects that did not test positive for either Norovirus GII or Norovirus GI at baseline will be excluded from the analyses. The first day of undetectable quantitative Norovirus PCR is the first day the subject had either a negative result or a result less than the lower limit of quantitation (LLOQ) for the viral load test type (Norovirus GII or Norovirus GI) that they initially tested positive for at baseline. Viral load will be quantified as the geometric mean of the replicates. Negative results will be imputed as $\frac{1}{2}$ the LLOQ and results greater than the upper limit of quantification (ULOQ) will be imputed as the ULOQ.

Initial Clinical Improvement in Norovirus Disease:

Initial clinical improvement in Norovirus disease through 28 and 180 days for at least 48 hours, is defined by:

- a. 50% reduction in number of episodes of vomiting and,
- b. Improvement in PO intake, as judged by the subjects and,
- c. 50% reduction in the number of episodes of diarrhea as classified by the subject by the Bristol Stool Chart as type 6 or 7 bowel movements.

The baseline values for number of episodes of vomiting and diarrhea will be the numbers provided on the first non-missing daily diary entry for the vomiting and diarrhea questions, respectively. Subjects must answer “yes” to the daily diary question “Did you eat your usual diet today?” to meet the improvement in PO intake criteria.

Detailed Patient-Reported Outcome (PRO) Measures:

Study personnel will administer detailed PRO questionnaires to subjects at Visit 01 (Day 1), Visit 05 (Day 28), Visit 08 (Day 60), Visit 10 (Day 120), and Visit 12 (Day 180).

Quality of Life.

Adult subjects will complete two questionnaires for quality of life: NNITS PRO EuroQOL-5 and NNITS PRO IBSQOL [\[30\]](#). There were no pediatric subjects enrolled in the study. The IBSQOL contains 34 items, each with a five-point response scale. The score for each subject/visit will be:

$$Score_{IBSQOL} = \frac{\text{The sum of the items} - \text{lowest possible score}}{\text{possible raw score range}} \times 100$$

If items are missing, confirm that at least 17 (50%) have been answered before calculating the score. If less than 17 questions have been answered, the score will be left as missing.

The scoring guide for the EuroQOL-5 questionnaire [31] states that a single index value is not currently possible. Instead, the levels will be dichotomized into ‘no problems’ (i.e. level 1) and ‘problems’ (i.e. levels 2 and 3).

Patient-Reported Physical Function:

Adult subjects will complete the NNITS PRO PROMIS [32] Physical Function questionnaire. The raw score will be the sum of the items from the questionnaire. The score for each subject/visit will then use the following table to convert the raw score into a t-score:

Physical Function 8b Short Form Conversion Table		
Raw Score	T-score	SE*
8	20.9	3.5
9	24.4	2.5
10	26.4	2.2
11	27.9	2.0
12	29.1	1.9
13	30.1	1.8
14	31.1	1.7
15	31.9	1.7
16	32.7	1.6
17	33.4	1.6
18	34.1	1.6
19	34.8	1.6
20	35.5	1.6
21	36.2	1.5
22	36.8	1.5
23	37.5	1.5
24	38.1	1.5
25	38.8	1.5
26	39.4	1.5
27	40.1	1.6
28	40.8	1.6
29	41.5	1.6
30	42.2	1.6
31	43.0	1.6
32	43.7	1.6
33	44.6	1.7
34	45.5	1.7
35	46.4	1.8
36	47.5	1.9
37	48.8	2.1
38	50.4	2.5
39	52.5	2.9
40	59.7	5.9

* SE = Standard error

Adult version

If items are missing, confirm that at least 4 (50%) have been answered before calculating the score. If less than 4 questions have been answered, the score will be left as missing. If less than 4 items are missing, the pro-rated raw score will be:

$$Raw\ score = \frac{Raw\ sum \times 8}{Number\ of\ items\ that\ were\ actually\ answered}$$

If the result is a fraction, round up to the nearest whole number.

Patient-Reported Emotional Distress:

Adult subjects will complete the NNITS PROMIS Emotional Questionnaire. Patient-reported emotional distress will be reported in three separate categories: depression, anxiety, and fatigue.

The raw score for depression will be the sum of questions #1-4. The depression score for each subject/visit will then use the following table to convert the raw score into a t-score:

Depression 4a Short Form Conversion Table		
Raw Score	T-score	SE*
4	41.0	6.2
5	49.0	3.2
6	51.8	2.7
7	53.9	2.4
8	55.7	2.3
9	57.3	2.3
10	58.9	2.3
11	60.5	2.3
12	62.2	2.3
13	63.9	2.3
14	65.7	2.3
15	67.5	2.3
16	69.4	2.3
17	71.2	2.4
18	73.3	2.4
19	75.7	2.6
20	79.4	3.6

*SE = Standard Error

All questions must be answered to receive a depression score.

The raw score for anxiety will be the sum of questions #5-8. The anxiety score for each subject/visit will then use the following table to convert the raw score into a t-score:

Anxiety 4a Short Form Conversion Table		
Raw Score	T-score	SE*
4	40.3	6.1
5	48.0	3.6
6	51.2	3.1
7	53.7	2.8
8	55.8	2.7
9	57.7	2.6
10	59.5	2.6
11	61.4	2.6
12	63.4	2.6
13	65.3	2.7
14	67.3	2.7
15	69.3	2.7
16	71.2	2.7
17	73.3	2.7
18	75.4	2.7
19	77.9	2.9
20	81.6	3.7

*SE = Standard Error

All questions must be answered to receive an anxiety score.

The raw score for fatigue will be the sum of questions #9-12. The fatigue score for each subject/visit will then use the following table to convert the raw score into a t-score:

Fatigue 4a Short Form Conversion Table		
Raw Score	T-score	SE*
4	33.7	4.9
5	39.7	3.1
6	43.1	2.7
7	46.0	2.6
8	48.6	2.5
9	51.0	2.5
10	53.1	2.4
11	55.1	2.4
12	57.0	2.3
13	58.8	2.3
14	60.7	2.3
15	62.7	2.4
16	64.6	2.4
17	66.7	2.4
18	69.0	2.5
19	71.6	2.7
20	75.8	3.9

*SE = Standard Error

All questions must be answered to receive a fatigue score.

Patient-Reported Gastrointestinal Symptoms:

Adult subjects will complete the NNITS PROMIS GI Questionnaire. For question 17, each belly pain area marked “yes” will indicate 1 point (e.g. if a subject answers “yes” for belly pain area 1, belly pain area 6, and belly pain area 8, their score for question 17 would be 3). The GI Questionnaire contains questions from four domains: diarrhea (questions 1 – 3 and 8 – 10), nausea (questions 4 – 7), fecal incontinence (questions 11 – 14), and belly pain (questions 15 – 20) and therefore cannot be summarized into a single score. Instead each domain will be reported separately. The raw scores for each domain will be the sum of the items from the questionnaire that are in the domain. The score for each subject/visit will then use the following tables to convert the raw scores into t-scores:

Diarrhea:

Raw score	T-score
0	38.3
1	43.3
2	45.9
3	48.2
4	50.1
5	51.9
6	53.3
7	54.5
8	55.6
9	56.7
10	57.8
11	58.8
12	59.8
13	60.7
14	61.6
15	62.5
16	63.5
17	64.4
18	65.5
19	66.6
20	67.9
21	69.2
22	70.8
23	72.3
24	75.2

Nausea:

Raw score	T-score
0	40.3
1	45.0
2	49.3
3	52.9
4	55.9
5	58.7
6	60.9
7	62.8
8	64.6
9	66.4
10	68.1
11	69.8
12	71.6
13	73.5
14	75.6
15	78.0
16	80.4

Fecal Incontinence:

Raw score	T-score
0	42.0
1	49.1
2	54.4
3	58.6
4	62.1
5	64.4
6	66.0
7	67.7
8	69.5
9	71.4
10	73.5
11	75.8
12	78.4
13	80.8
14	80.8
15	80.8
16	80.8

Belly Pain:

Raw score	T-score
0	31.7
1	37.2
2	40.6
3	43.5
4	46.2
5	48.6
6	50.7
7	52.6
8	54.3
9	55.9
10	57.5
11	59.1
12	60.5
13	61.9
14	63.2
15	64.5
16	65.8
17	67.0
18	68.3
19	69.5
20	70.8
21	72.1
22	73.5
23	74.9
24	76.1
25	76.9
26	77.9
27	78.6
28	78.6
29	82.1

If items are missing, confirm that at least 50% have been answered before calculating the score. If less than 50% of the questions have been answered, the score will be left as missing. If less than 50% of the items are missing, the pro-rated raw score will be:

$$\text{Raw score} = \frac{\text{Raw sum} \times \text{Total number of questions in domain}}{\text{Number of items that were actually answered}}$$

If the result is a fraction, round up to the nearest whole number. Note that only three of the four nausea questions from the GI questionnaire were included, therefore in order to meet the 50% criteria at least 2 of the 3 questions must be answered.

Positive and Negative Affect Scale (PANAS):

Adult subjects will complete the NNITS PROMIS PANAS Questionnaire. Patient-reported positive and negative affect scores will be reported in two separate categories: positive affect score and negative affect score.

The score for positive affect will be the sum of questions #1, 3, 5, 9, 10, 12, 14, 16, 17, and 19. The score for negative affect will be the sum of questions #2, 4, 6, 7, 8, 11, 13, 15, 18, and 20.

Reduction in Amount of Antimotility Agents:

The amount of antimotility agents for a given day will be defined as the response to the “# of antidiarrheals today” question in the Phase 1 (Treatment Phase) Daily Symptom Diary. Missing responses will be left as missing. 50% reduction in the amount of antimotility agents will be defined as the first study day in which the subject’s response was less than or equal to 50% of their response given on Day 1.

Number of Days of Diarrhea:

The number of days of diarrhea will be based on the Daily Diary Diarrhea Questions (see above). For a day to count towards the number of days of diarrhea, one of the following must occur: a quantitative diarrhea question must be greater than 0 or a qualitative question must be marked “yes”. Missing responses will be left as missing.

Number of Type 6 or 7 Stools:

The number of Type 6 or 7 stools through Day 28 will be defined as the sum of the responses to the quantitative Daily Diary Diarrhea Questions during the Treatment Phase (see above). Missing responses will be left as missing.

Number of Days of IV Hydration or Total Parenteral Nutrition (TPN) Therapy:

The number of days of IV hydration or TPN therapy will be defined as the number of days with a concomitant medication with any indication related to IV hydration or TPN therapy. A blinded review of the concomitant medication data will be performed by the Medical Monitor to identify medications that should be included in the analysis. Days prior to Day 1 will not be included in the calculation of the number of days. Medications that are ongoing after Day 28 will be censored at 28 days.

Co-pathogen Status:

Co-pathogen status will be determined by the BioFire stool pathogen screen on Days 1 and 180. Co-pathogen status will be determined on Days 7, 14, 21, 28, 60, 120, and with recurrent diarrhea if unformed stool is present on study day. Analyses will only include whether pathogens were detected or not and will not differentiate by co-pathogen type. The listing will include which co-pathogens were detected at each subject/visit ([Listing 18](#)).

Secretor Status:

Saliva is collected at screening to determine H type 1 secretor status (phenotyping), while a buccal swab is collected to perform FUT2 genotyping. Phenotype and genotype results will either be “secretor” or “non-secretor” for each subject.

Norovirus-Specific Immunoglobulins (Ig):

Results below the lower limit of detection (LLOD) will be imputed as $\frac{1}{2}$ the LLOD. Results above the upper limit of detection (ULOD) will be imputed as the ULOD.

Responders:

A subject is classified as a responder if he or she has a four-fold or greater increase in Norovirus-specific Ig titers compared to baseline (Day 1).

Study Day:

Study day will be reported as the number of days from randomization with the day of randomization reported as study day 1.

Days Post-Randomization:

Days post-randomization will be reported as the number of days since randomization; if an event began on the day of randomization, the days post-randomization is reported as 0.

Duration:

Duration will be reported as the difference between the start and end dates, inclusive of the day the event started.

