5.3.4 Handling of Withdrawals

Subjects who withdraw or are withdrawn from participation in the study at any time. Subjects may also withdraw voluntarily from receiving the study intervention for any reason. An investigator may also withdraw a subject from receiving further intervention

Subjects who withdraw, or are withdrawn from the efficacy endpoint analysis, or are lost to follow-up after signing the informed consent form, randomization, and receipt of study product will not be replaced. Subjects who withdraw consent after signing the informed consent form and randomization but before receipt of study product may be replaced.

If a subject withdraws from the study after receiving any amount of study drug the subject will be asked to continue scheduled study procedures including safety and efficacy evaluations, if possible, and be given appropriate care under medical supervision if symptoms of any AE related to participation in the study are continuing. The participant will be followed until the AE is resolved or until the subject's condition becomes stable.

Subjects who request to withdraw their consent after study treatment from further participation in the study will be reminded of the importance of continuing the study for safety evaluations and will be encouraged to complete the Early Termination Visit if they choose not to complete the remaining study visits. The Early Termination Visit procedures are listed in Section 7.4. Subjects who choose to decline continuation in study participation will no longer be contacted for follow-up.

If a subject is withdrawn at any time due to an AE, the event will be followed until it is resolved or in the opinion of the Investigator is determined medically stable with the consent from the subject. The site PI may request unblinding of the study drug assignment if they feel that such information is essential for the management of an AE or SAE. If the PI feels that unblinding is essential for management of the AE or SAE, they will request unblinding by contacting the DMID Medical Monitor. Clinical failure is not an acceptable reason to request unblinding.

Refer to the MOP and the DMID policy "Unblinding Individual Participants in DMID Clinical Research," the current policy is available at <https://www.niaid.nih.gov/research/dmid-data-management>.

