4.5.1. Efficacy Variables

The primary efficacy variables to be assessed are the cessation of vomiting and no stools classified by the Bristol Stool Chart as diarrhea (Type 6 or 7) and are based on outcomes reported in the Subject Daily Diary. The subject diaries were prepared by Northwestern University. They will be reviewed and collected at every visit, including unscheduled or early termination visits. The Subject Daily Symptom Dairies will be completed by the subject daily, in real-time, from Day 1 through Day 180. All diaries should be completed at the same time every day, when possible. Subjects will complete the NNITS Daily Symptom Diary [Day 1 – 28] from the time of study treatment dispensation until visit 05. At visit 05 (Study Day 28), subjects will complete the NNITS Daily Symptom Diary – Post Treatment [Day 29 – 180].

The exploratory efficacy variables for the following outcome measures are also based on subject daily diaries:

- Time from randomization to initial clinical improvement in Norovirus disease through 28 and 180 days for at least 48 hours.
- Time from randomization to initial cessation of vomiting through Day 180 (recurrent vomiting will be considered disease recurrence unless determined to be due to another etiology [i.e. GVHD]).
- Time from randomization to subject report of no loss of appetite that is maintained for 48 hours through Day 180 (measure will be first time that the subject reports that they have no “loss of appetite” on their daily diary).
- Time from randomization to initial cessation of diarrhea through Day 180 classified by the Bristol Stool Chart as type 6 or 7 bowel movements (recurrent diarrhea will be considered disease recurrence unless determined to be due to another etiology [i.e. GVHD]).
- Time from randomization to 50% reduction in the amount of antimotility agents utilized by the subject through Day 180.
- Number of days of diarrhea through Days 28 and 180.
- Number of stools classified by the Bristol Stool Chart as type 6 or 7 bowel movements through Day 28.
- Number of days of IV hydration or total parenteral nutrition (TPN) therapy through Day 28.

The secondary efficacy variable to be assessed is viral load and is based on stool for Norovirus assays. Norovirus viral load assays will be performed in the [name] Laboratory (CCHMC, Cincinnati, OH) and will be measured using Quantitative RT-PCR (qRT-PCR) at Study Days 1, 7, 14, 21, 28, 60, 120, 180, and with recurrent diarrhea.

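### A blank answer to the re-dosing question makes an otherwise symptom-free treatment-phase day fail the primary resolution rule, which may date resolution late in subjects who stop or skip study drug

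*SAP*

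**What the plan says.** Protocol 3.2.1 and SAP 3.2.1 define clinical resolution by symptoms alone: vomiting has ceased and there are no Bristol Type 6 or 7 stools. SAP 3.3 makes this operational: "Subjects will need to have at least two consecutive daily diary entries where they reported no vomiting" and no Type 6 or 7 stool.

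The treatment-phase diary has two vomiting items. One is a count, "How many times did you vomit today". The other is labelled qualitative, "Did you have to take another dose because you threw up the first dose within 1 hour". For a treatment-phase day to count, SAP 3.3 requires:

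- both stool counts at 0;
- for the stool items on too many to count, "Both qualitative diarrhea questions must be missing (i.e. not" 'yes');
- the vomiting count at 0;
- "The qualitative vomiting question must be" 'no'.

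SAP 4.5.1 has subjects use this diary "from the time of study treatment dispensation until visit 05", which is scheduled at Day 28 +3. On stopping early, Protocol 5.3.4 states: "If a subject withdraws from the study after receiving any amount of study drug the subject will be asked to continue scheduled study procedures", and it includes efficacy evaluations in those procedures. SAP 6.3.1 keeps everyone who took at least one dose in the mITT population.

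**The concern.** The re-dosing question is about handling a dose, not about a symptom. A subject who took no dose that day has nothing to repeat and may leave it empty. Read as written, that blank fails a day which meets the protocol's own definition of resolution. The stool items in the same list are not treated this way.

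The rule defines the event for the only primary endpoint. It also carries into the per-protocol, worst-case, subgroup, co-pathogen and secretor analyses. Any error falls on subjects who are not taking drug. Protocol 2.1 describes the drug's adverse reactions as mainly gastrointestinal, so stopping could differ by arm, although neither document gives stopping rates. With 31 subjects split into acute and chronic strata, one event moved by about three weeks could be visible in a stratum median or a Kaplan-Meier curve.

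**Working it through.** **1. The same day under each rule.** Take a treatment-phase day with stool counts 0, vomiting count 0, the stool tick items blank and the re-dosing item blank.

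| Source | Does the day count? |
|---|---|
| Protocol 3.2.1 and SAP 3.2.1 (no vomiting, no Type 6/7 stools) | Yes |
| SAP 3.3, stool items (blank accepted) | Passes |
| SAP 3.3, vomiting count (0) | Passes |
| SAP 3.3, re-dosing item (must be 'no') | Fails |

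**2. Can the blank occur?** SAP Listing 12 shows the item as Yes/No, with missing values displayed as a dash and no 'not applicable' level. Protocol 7.1 ties diary completion to the time of dosing. SAP 4.4.5 tells subjects to skip a missed dose. A blank is therefore foreseeable, but neither document says it is usual.

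**3. Does SAP 6.5 repair it?** SAP 3.3 refers to 6.5 only when a whole diary entry is missing. Section 6.5 speaks of a gap in outcome data and does not say whether one blank item is a gap. Suppose it is, and a subject is off drug and symptom-free from Day 6, leaving the item blank through Day 28:

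- Day 5 symptomatic, Day 29 clean: the two sides differ, so the gap is imputed symptomatic and the delay remains.
- Day 5 clean with 'no', Day 29 clean: the gap is imputed clean and resolution goes to the median of Days 6–28, which is Day 17. That is 12 days after the first clean day.

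So the gap rule helps only some subjects, and only in part.

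**4. Delay in the worst single case.** The subject is symptomatic to Day 5, off drug and clean from Day 6, with blanks throughout. By the definition, resolution starts on Day 6. Under the rule as written, the first day that can count is Day 29 if visit 05 falls on Day 28, or Day 32 if it falls on Day 31. The delay is 29 − 6 = 23 to 32 − 6 = 26 days. One isolated skipped day costs only a day or two.

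**5. Design figures.** Planning medians (SAP 5) are 135 days on placebo and 67.5 on nitazoxanide, which gives a hazard ratio of 2 if times are exponential. P(resolved by Day 180) is 1 − 2^(−180/135) = 0.603 and 1 − 2^(−180/67.5) = 0.843, mean 0.723. With 128 subjects that is 128 × 0.723 = 92.5 events. Power = Φ(√92.5 × ln 2 / 2 − 1.96) = Φ(1.37) = 91.5%. The SAP states 90%, and 91.3% by simulation, so its figures reproduce.

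**6. Expected number affected.** Assumptions not in the documents: a fraction f stops drug on a day uniform over Days 3–20 (midpoint 11.5); every one leaves the item blank; every blocked resolution moves to Day 29. The share of stoppers affected is about 2^(−11.5/m) − 2^(−29/m) for median m.

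- Planning medians: placebo 0.943 − 0.862 = 0.081; nitazoxanide 0.889 − 0.742 = 0.146 (unrounded); mean 0.114. With f = 5–15% this is 0.6–1.7% of subjects, or 0.2–0.5 of 31.
- Much shorter medians of 18 and 9 days (assumed): placebo 0.642 − 0.327 = 0.315; nitazoxanide 0.412 − 0.107 = 0.305; mean 0.310. With f = 5%, 10% and 15% on average over the arms, this is 0.5, 1.0 and 1.4 of 31.

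**7. Effect on the comparison** (same blanking assumptions, by simulation).

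- Planning medians, 15% against 5% stopping in either direction: the hazard ratio changes by less than 0.01.
- Medians of 18 and 9 days: 2.00 becomes 1.94–1.95 with 15% stopping on nitazoxanide and 5% on placebo, and 2.03–2.04 with the rates reversed.
- Planning medians, 64 per arm, 0–30% stopping on a day uniform over Days 1–28: power is 91.2–91.8%, against 91.8% with no stopping. The differences are within simulation error.

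**The case against.** A reader might infer that subjects off study drug cannot resolve before Day 29. The documents do not support that.

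- The item is Yes/No, and a subject who took no dose can truthfully answer 'no'. The diary form and its instructions are in the manual of procedures, which is not among the documents.
- A subject with two clean days before stopping is already an event.
- If blanks count as a gap, SAP 6.5 may place resolution earlier.
- The diary changes at visit 05, not on a fixed Day 29. That date also needs a charitable reading of the longitudinal rule, which says "The quantitative vomiting question must be 0" although that diary asks only a yes/no vomiting question.

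All four points stand. They make the delay conditional, but they do not remove the rule that causes it.

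The different treatment of the stool items may also be deliberate. 'Must be missing' suits a tick-only box, and 'must be no' suits a Yes/No field. The SAP was written after enrolment stopped and after manual review of diary data (SAP 6.6 and 14.1.3). That may explain the wording, but it still leaves a blank in the Yes/No field scored as a failed day.

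Nor is the item worthless. If the diary is completed at dosing, a dose vomited afterwards may be absent from the count, and a 'yes' would catch it. The fix should therefore keep 'yes' as disqualifying.

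Finally, the numerical effect is negligible at the planning medians, its direction is unknown, and SAP 14.2 calls the analyses primarily descriptive. This argues against a high severity.

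**Conclusion.** The point holds in limited form. SAP 3.3 fails a symptom-free treatment-phase day because of a blank on a dosing-dependent item, and this departs from the endpoint definition. The primary event may be dated late in subjects who stop or skip drug and leave the item empty. In the extreme case the delay runs to the start of the longitudinal diary, about 23–26 days in the example.

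How often this happens is unknown. Under assumed stopping rates of 5–15% and universal blanking, it affects fewer than one of 31 subjects at the planning medians and about one at much shorter medians. The hazard ratio changes by less than 0.01 at the planning medians. The stopping rates, the blanking and the shorter medians are all assumptions. The reason to act is that the derivation of the primary event should match its definition, not that the result is likely to change. Severity: minor to should-fix.

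**What to change.** In SAP 3.3, change the treatment-phase requirement for the re-dosing item to: must not be 'yes' (no or missing), with number of vomiting episodes equal to 0 as the operative criterion. This matches the stool items. It costs one phrase and one line of derivation code, and should be settled before unblinding.

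The downside is that a blank on a day when a dose was vomited after the diary was completed would count as clean.

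Two small additions fit the same edit. State in SAP 6.5 whether a single blank item in a completed entry is a gap. Reword the longitudinal vomiting requirement so that it refers to the yes/no question that diary contains. A count by arm of treatment-phase days on which only the re-dosing item is blank, taken from the data behind Listing 12, would show whether the issue arose at all.
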